### 3.3. Data collection

For all consecutive eligible patients included in the study from each participating Institution, their medical records will be retrieved and anonymized data entered into a database. The following information will be collected, if available:

- 1) Baseline characteristics: body mass index; smoking habit; age at menarche; age at menopause; menopausal status at the time of breast cancer diagnosis; use of birth control pills; prior children before breast cancer diagnosis; history of spontaneous abortion; history of induced abortion; prior treatment for infertility; prior gynecological surgery and/or medical history with possible impact on fertility.
- 2) Breast cancer history: date of diagnosis; age at diagnosis; disease stage; laterality of the primary tumor; type of breast and axillary surgery; use of breast reconstruction surgery; grade; histology; tumor size and nodal status (for patients who underwent primary systemic therapy, only clinical tumor size and nodal status will be collected); hormone receptor status (estrogen and progesterone receptors); HER2 status.
- 3) Treatment of the primary tumor: timing of systemic therapy administration; use of chemotherapy (type and number of cycles); use of endocrine therapy (type and duration); use of anti-HER2 targeted therapy (type and duration); use of radiotherapy.
- 4) Survival status: any recurrence of invasive breast cancer including date of the event; any second primary breast cancer including date of the event; any second primary malignancy including date of the event; date of last follow-up and/or death; cause of death (breast cancer-related or not).
- 5) Ovarian function after chemotherapy: treatment-induced POF; age at menopause.

6) Pregnancy after breast cancer: any pregnancy including date of the event; pregnancy outcome; gestational age at delivery; any pregnancy/fetal/birth complications; breastfeeding and its duration; use and type of ART.

7) BRCA mutation: date of *BRCA* testing; type of *BRCA* mutation; use and date of breast prophylactic surgery; use and date of gynecological prophylactic surgery.

8) Additional information: diagnosis of breast cancer during pregnancy, availability of digital scanned images for TILs analysis

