To evaluate the safety of ART procedures following breast cancer diagnosis in *BRCA* mutated survivors, two groups of patients within the pregnant cohort will be considered: patients who achieved pregnancy with the use of any ART procedure (i.e. “ART group”) and patients who achieved pregnancy without the use of any ART procedure (i.e. “no ART group”). A subgroup analysis will be performed to evaluate the safety of controlled ovarian stimulation as part of ART within the ART group.

In patients who underwent chemotherapy as part of (neo)adjuvant systemic therapy, the impact of anticancer therapies (i.e. chemotherapy) on patients’ ovarian function, in terms of incidence of treatment-induced POF and age at menopause will be evaluated, if available. According to the World Health Organization definition of postmenopausal status [23], treatment-induced amenorrhea will be defined by the absence of menses for  $\geq$  12 months after the end of chemotherapy. Age at menopause will be defined as age in which patients had absence of menses for  $\geq$  12 months. For patients who

developed treatment-induced amenorrhea but then had a recovery of menses more than 12 months after the end of chemotherapy and with active menstrual function within 12 months prior to the last follow-up visit, they will not be considered as having developed menopause. Subgroup analyses will be performed according to age at diagnosis, type of chemotherapy used (anthracycline- and taxane-based regimens vs. anthracycline-based regimens vs. other regimens), and use of endocrine therapy (yes vs. no). These results will be compared to historical data in the *BRCA* wild-type breast cancer population.

Considering the sample size and the uniqueness of the young cohort of *BRCA* mutated patients expected to be included in the study, additional analyses will be conducted to describe baseline, tumor and treatment characteristics as well as patterns of care including access to risk-reducing surgeries. Possible changes over time will be also assessed. Moreover, similarly, the prognostic impact of baseline, tumor and treatment characteristics as well as of risk-reducing surgeries in *BRCA* mutated patients will be also evaluated.

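### The amenorrhea rule has no premenopausal entry condition and no provision for ovarian suppression, so incidence overall and in the endocrine-treated subgroup can only be biased upward as a measure of chemotherapy's effect

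*Combined protocol and SAP*

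**What the plan says.** Section 2 lists a secondary objective on anticancer therapies and ovarian function, measured by treatment-induced premature ovarian failure (POF) and age at menopause. Section 4 narrows this to "the impact of anticancer therapies (i.e. chemotherapy) on patients’ ovarian function". Its population is given as "In patients who underwent chemotherapy as part of (neo)adjuvant systemic therapy", with no condition on menopausal status. The event rule is that "treatment-induced amenorrhea will be defined by the absence of menses for" 12 months or more after the end of chemotherapy.

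Two provisions bear on the problem:

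- **Recovery exception.** Women whose menses return more than 12 months after chemotherapy, and who are menstruating within the 12 months before their last visit, are set apart: "they will not be considered as having developed menopause".
- **Endocrine subgroup.** Results are to be shown by use of endocrine therapy, yes or no.

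Section 4 then adds: "These results will be compared to historical data in the" BRCA wild-type breast cancer population. It neither identifies those data nor requires the same definition.

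Section 3.3 collects "menopausal status at the time of breast cancer diagnosis" and the type and duration of endocrine therapy. Section 4 uses neither menopausal status nor endocrine type and duration in the event or the denominator. The eligibility criteria in section 3.1 set an upper age of 40 at diagnosis but no menopausal criterion.

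**The concern.** The stated target is the effect of chemotherapy on the ovary. Followed as written, the rule also counts two kinds of women for whom chemotherapy need not be the cause:

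- A woman already menopausal at diagnosis has no menses before, during or after chemotherapy, so she meets the 12-month rule.
- A woman on ovarian-suppressing endocrine therapy has no menses while it continues. That some endocrine therapy works this way is general clinical knowledge; the documents name no agents. If she is still treated at her last visit, she cannot show the recovery that the exception requires.

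The endocrine-treated subgroup would mix continuing treatment with ovarian damage, and the pooled incidence would carry the same mixture. Section 1 raises the possibility that carriers are more sensitive to gonadotoxic chemotherapy, so an incidence that is too high could be read as support for that idea.

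**Working it through.** The plan states no rate, sample size or power for this objective, so there is no figure to reproduce. The check is first of the text, then of direction and possible size.

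**Text**

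| Element | What is stated | Removes menopausal at diagnosis? | Removes suppressed at last visit? |
|---|---|---|---|
| Eligibility (3.1) | Age 40 or under | No | No |
| Population (4) | All given (neo)adjuvant chemotherapy | No | No |
| Event (4) | No menses for 12 months or more after chemotherapy | No | No |
| Recovery exception (4) | Menses returned and recently active; concerns the menopause label | No | No |
| Endocrine subgroup (4) | Yes or no; not by type or by treatment status at assessment | No | Separates, but does not correct the pooled figure |

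**Direction**

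Let p be the true chemotherapy-induced incidence, m the share menopausal at diagnosis, and s the share of the remaining women without menses because of suppression. The documents give none of the three, so all are assumptions. The suppressed women are taken to have the same underlying p as the others.

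- Counted incidence = m + (1 − m) × [s + (1 − s) × p]
- Counted incidence − p = (1 − p) × [1 − (1 − m)(1 − s)]

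The second expression is never negative, so these two mechanisms can only raise the figure.

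**Possible size, with p = 20%**

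- Suppression alone (m = 0): s = 5% gives 0.05 + 0.95 × 0.20 = 24.0%; s = 30% gives 0.30 + 0.70 × 0.20 = 44.0%.
- Baseline menopause alone (s = 0): m = 1% gives 0.01 + 0.99 × 0.20 = 20.8%; m = 3% gives 0.03 + 0.97 × 0.20 = 22.4%.
- Both, with m = 1%: s = 5% gives 0.01 + 0.99 × 0.24 = 24.8%; s = 30% gives 0.01 + 0.99 × 0.44 = 44.6%.

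**Counted incidence over a wider range**

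| p | m | s = 0 | s = 5% | s = 15% | s = 30% |
|---|---|---|---|---|---|
| 10% | 0 | 10.0% | 14.5% | 23.5% | 37.0% |
| 10% | 3% | 12.7% | 17.1% | 25.8% | 38.9% |
| 20% | 0 | 20.0% | 24.0% | 32.0% | 44.0% |
| 20% | 3% | 22.4% | 26.3% | 34.0% | 45.7% |
| 40% | 0 | 40.0% | 43.0% | 49.0% | 58.0% |
| 40% | 3% | 41.8% | 44.7% | 50.5% | 59.3% |

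The counted figure runs from 1.0 to 3.9 times the true one (38.9/10 = 3.89). Suppression drives it; baseline menopause adds little.

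**Endocrine subgroup**

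Take p = 20% in both subgroups, m = 0, and s = 30% among endocrine-treated women. The plan would report 44% with endocrine therapy and 20% without, although the chemotherapy effect is identical.

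**The case against.** The strongest reply has five parts.

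1. **The outcome is called treatment-induced, and section 1 speaks of premenopausal patients.** On ordinary reading, a woman already menopausal does not qualify. Sites also record treatment-induced POF as an item and may already leave her out. This has some force, and at age 40 or under the group is probably small. But section 4 defines its term by the 12-month rule alone, and nothing tells sites to make the exclusion, so practice may vary.
2. **A nearly clean estimate is already planned.** The subgroup without endocrine therapy is largely free of suppression. That stands. It does not repair the pooled figure or the endocrine-treated subgroup. Section 4 also plans multivariate logistic regression for dichotomous outcomes, but covariate adjustment does not correct an event that is itself misclassified.
3. **The objective in section 2 covers anticancer therapies generally, so drug-maintained amenorrhea might belong.** Section 4 closes that reading by equating anticancer therapies with chemotherapy.
4. **Every share is assumed.** This stands in full. A reader might infer from the illustration that the overstatement is known to be large; the documents give neither the number of women suppressed nor the duration.
5. **The wild-type comparison may not be biased.** This also stands. A reader might infer that the comparison will wrongly favor greater sensitivity in carriers. If the historical data use the same rule and a similar population, the inflation may partly cancel, and changing the definition on one side only could create a mismatch. The plan neither identifies those data nor ensures alignment.

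**Conclusion.** The concern holds as a one-directional bias in a stated rule. It affects the overall incidence and the endocrine-treated subgroup. It does not materially affect the subgroup without endocrine therapy, apart from any women menopausal at diagnosis. The size is unknown: the figures above show direction and sensitivity under assumed shares, not an estimate for this study. The suppression part rests on general clinical knowledge that some endocrine therapy stops menses.

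A reader might also infer that the remedy is simply to restart the 12-month clock when suppression ends. The documents do not support that as the main analysis. Section 3.3 lists no end date for chemotherapy, no start or stop dates for endocrine therapy and no dates of menses. Deferring the clock would also assess those women at older ages and select by treatment duration and recency of diagnosis.

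The change is worth making before the analysis because it is cheap and removes an avoidable bias. It concerns one secondary objective, evaluated where data exist, and does not touch DFS, BCSS, OS or the pregnancy rate. Prophylactic gynecological surgery raises a similar question but is a separate matter.

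**What to change.** Amend the ovarian-function paragraph of section 4 as follows.

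1. Restrict the analysis to women recorded as premenopausal at diagnosis, and give the number excluded or with status missing.
2. Use the collected endocrine type and duration to identify women given ovarian-suppressing therapy. Report them separately, or as not evaluable where they were still on it at assessment, and give their number.
3. Take the headline chemotherapy-related incidence from the remaining women.
4. Where possible, compare with historical wild-type data that use the same definition and population; otherwise state the mismatch beside the comparison.
5. Restart the 12-month window at the end of suppression only as a sensitivity analysis, for women whose dates can be obtained.

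**Cost.** Steps 1 and 3, and separate reporting in step 2, use listed fields, although all items are collected only where available. Deciding who was still on therapy may need an approximation from duration and follow-up, or a query to the site. Step 5 needs dates that section 3.3 does not list. The evaluable denominator shrinks, mainly among receptor-positive women, so the headline figure represents them less well, and the report should say so.

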Concerns about fertility preservation and future chance of achieving a pregnancy are prevalent issues affecting young breast cancer patients [8]. Hence, accordingly, major international guidelines recommend physicians to address with patients as part of informed consent before anticancer therapies the possibility of developing POF and infertility, and then to discuss fertility preservation options in interested patients [9–11]. Specific issues on this regard should be considered in patients with *BRCA* mutation in the context of their unique concerns [12]. For carriers, given the increasing risk of ovarian cancer with age, bilateral salpingo-oophorectomy is generally recommended for both *BRCA1* and *BRCA2* carriers between the ages of 35 and 40 years and upon completion of childbearing [13]. Moreover, some carriers wish to eliminate the mutation from future offspring through pre-implantation genetic diagnosis [14]. Finally, given the increasing risk of ovarian and breast cancer and the risk of developing long-term treatment-related POF [15], the window for fertility and pregnancy may be narrow in such young women. Of note, although, the last years have brought many safety and efficacy data on the available options for fertility preservation increasing the chances of

future offspring in cancer survivors, numerous challenges remain for young breast cancer patients considering fertility preservation and to have a pregnancy after the end of treatments, especially for those with *BRCA* mutations. Thus, further research is needed in the field; particularly, reproduction studies to address the specific issues of women with *BRCA* mutations are lacking and should be considered a research priority.

Approximately 40% to 50% of women in whom breast cancer is diagnosed during childbearing age wish to have a subsequent pregnancy [16]. However, the percentage of breast cancer patients reported in the literature that has at least one full-term pregnancy after breast cancer diagnosis is very low. Of note, among cancer survivors, breast cancer patients have the lowest pregnancy rate with an overall 67% reduction in the chance of giving birth after cancer treatment as compared to the general population [17]. This observation reflects not only the damage to ovarian reserve due to the gonadotoxic treatments required, but also patient and provider concerns related to a possible negative impact of pregnancy on the evolution of breast cancer [18].

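### Treatment-induced amenorrhea and age at menopause are defined without regard to cause, so surgical menopause can enter both and distort the comparison with BRCA wild-type data

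*Combined protocol and SAP*

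**What the plan says.** The ovarian-function analysis in Section 4 covers women who had chemotherapy as part of (neo)adjuvant treatment. For them, "treatment-induced amenorrhea will be defined by the absence of menses for" 12 months or more after chemotherapy ends. The second endpoint follows the same pattern: "Age at menopause will be defined as age in which patients had absence of menses for" 12 months or more.

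There is one exception. Women whose menses came back more than 12 months after chemotherapy, and who were still menstruating in the year before their last visit, are set aside: "they will not be considered as having developed menopause".

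The planned subgroups are age at diagnosis, chemotherapy regimen and endocrine therapy (yes or no). Risk-reducing surgery is not among them. Section 4 mentions such surgery only under patterns of care and prognosis. On the comparator the plan says: "These results will be compared to historical data in the" BRCA wild-type breast cancer population.

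Two other places bear on this. Section 1 notes that "bilateral salpingo-oophorectomy is generally recommended for both" BRCA1 and BRCA2 carriers, at 35 to 40 years and once childbearing is complete. Section 3.3 collects "use and date of gynecological prophylactic surgery", but no ovarian-function definition uses that item.

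**The concern.** The objective is the effect of anticancer therapy on ovarian function, and Section 4 narrows this to chemotherapy. A woman whose ovaries have been removed has no menses whatever chemotherapy did to her, yet a definition based on absence of menses alone does not separate her from a woman with chemotherapy-induced failure.

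This matters more here than in most breast cancer cohorts. Every patient is a carrier diagnosed at 40 or younger, and the protocol itself describes the surgery as generally recommended for carriers at about that age. The documents give carrier status as the reason for the surgery, so they offer no ground to expect it to a similar extent in a wild-type series.

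The error would therefore fall mainly on one side of the comparison. It would also point towards the suggestion in Section 1 that carriers may be more sensitive to the gonadotoxic effect of chemotherapy.

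**Working it through.** The plan gives no rate, sample size or power for ovarian function, so there is no stated figure to reproduce. The check has two parts: how the definitions classify surgical cases, and an illustration of size.

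**1. Classification by timing of bilateral oophorectomy**

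| Timing of surgery | Treatment-induced amenorrhea | Age at menopause |
|---|---|---|
| Before or within 12 months after the end of chemotherapy, menses not resumed | Definition met | Set by surgery if she was not already menopausal |
| After menses have resumed | Wording ambiguous | Set by surgery |
| After 12 months without menses have already passed | Already counted; surgery adds nothing | Already set |

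The recovery exception rescues no surgical case. It also requires menses in the year before the last visit. A woman who recovered late and then had surgery more than 12 months before that visit therefore does not meet it.

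The direction is fixed for each endpoint. Surgical cases can only raise the amenorrhea proportion, and can only bring forward the recorded age at menopause.

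**2. Illustration of size for the amenorrhea proportion**

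Both inputs are assumptions, since the documents give neither:

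- p: the proportion who would have chemotherapy-induced amenorrhea.
- b: the proportion with bilateral oophorectomy before or within the 12-month window.

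Reported proportion = p + b − overlap. Under independence the overlap is p × b, so reported = 1 − (1 − p)(1 − b). With full overlap, reported = max(p, b). With no overlap, reported = p + b.

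For p = 20% and b = 20%:

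- Independence: 1 − 0.80 × 0.80 = 36%. The odds ratio against the true rate is (0.36/0.64)/(0.20/0.80) = 2.25.
- Full overlap: 20%.
- No overlap: 40%.

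Reported proportion under independence, with the range from full to no overlap:

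| True p | b = 10% | b = 20% | b = 30% |
|---|---|---|---|
| 10% | 19% (10–20) | 28% (20–30) | 37% (30–40) |
| 20% | 28% (20–30) | 36% (20–40) | 44% (30–50) |
| 40% | 46% (40–50) | 52% (40–60) | 58% (40–70) |

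**3. Effect of restricting to women with ovaries in place**

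Estimate = (p − overlap)/(1 − b). For p = b = 20%:

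- Independence: (0.20 − 0.04)/0.80 = 20%, the true value.
- No overlap: 0.20/0.80 = 25%.
- Full overlap: 0/0.80 = 0%.

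The restriction recovers p only if surgery is unrelated to ovarian failure. If the two are related, the restricted estimate is biased as well.

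**The case against.** The strongest reply is that nowhere does the plan say that oophorectomy counts as chemotherapy damage. The endpoint is called treatment-induced throughout. Section 3.3 records premature ovarian failure and prophylactic gynecological surgery as separate items, so a site may well leave surgical cases out of the former. The definition also invokes a World Health Organization source that may deal with surgical menopause. This is fair as far as it goes: a reader might infer that the plan deliberately attributes surgery to chemotherapy, and the documents do not support that. But neither the label nor the citation puts an exclusion into the text, and Section 3.3 lists no item for the cause of amenorrhea. At best, sites will classify differently. Age at menopause does not carry the label at all.

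Timing is a second fair point. Section 1 ties the surgery to age and completed childbearing, not to the end of chemotherapy. It would be wrong to infer that every oophorectomy inflates the amenorrhea rate; the wording clearly captures only surgery before or within the 12-month window. The case is stronger for age at menopause.

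Third, one might extend the argument to endocrine therapy that suppresses menses. That is partly addressed by the planned yes/no subgroup, and nothing in the documents makes it specific to carriers. It is not part of this point.

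Finally, this is one secondary objective, assessed where data are available, with no named comparator dataset or test. That limits the consequence but does not remove the defect.

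**Conclusion.** The point stands in this form. Both definitions ignore cause, their single exception cannot apply after bilateral oophorectomy, and the protocol expects that surgery in this population. Followed as written, they bias age at menopause downward and can bias the treatment-induced amenorrhea rate upward. An apparent excess over wild-type patients could then arise without any true difference in sensitivity to chemotherapy.

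Confidence is high that the rule is missing and in the direction of the error. It is not high on size. The 36% for a true 20% rests on an assumed 20% surgical share and on independence, and overlap alone moves it between 20% and 40%. A reader might take such figures as the expected bias in this study; the documents give no surgical share, failure rate or age distribution to support that. The primary DFS comparison is not affected. The change should be made before the ovarian-function analysis.

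**What to change.** In Section 4:

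- Count treatment-induced premature ovarian failure only in women with ovaries in place through the 12-month window, and say how surgery after menses have resumed is classified.
- For age at menopause, censor at bilateral oophorectomy or treat it as a competing event.
- Report surgical menopause as a separate category.
- Compare with wild-type data only where the historical source handles surgical menopause in the same way; otherwise state this as a limitation. Section 4 does not promise patient-level wild-type data, so the same rule may not be applicable to them.

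The cost is mainly wording, because use and date of gynecological prophylactic surgery are already collected. Three things need care. Section 3.3 does not list the type of operation, so the sponsor should first confirm that the record identifies bilateral oophorectomy. It lists neither the end date of chemotherapy nor dates of menses, so the window may have to be approximated. Fewer women will be evaluable, and exclusion or censoring may be informative if ovarian failure influences the decision to operate, so the number removed and this assumption should be reported.

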### Secondary objectives:

- To evaluate the prognostic impact (in terms of DFS, BCSS and OS) of pregnancy following breast cancer diagnosis in various subgroups of *BRCA* mutated patients according to:
  - Type of *BRCA* mutation: *BRCA1* vs. *BRCA2*;
  - Hormone receptor status: positive vs. negative;
  - HER2 status: positive vs. negative;
  - Exposure to chemotherapy: prior exposure vs. no prior exposure;
  - Exposure to endocrine therapy: prior exposure vs. no prior exposure;
  - Interval between diagnosis and pregnancy:  $\leq 2$  years vs.  $> 2$  years after diagnosis;
  - Outcome of pregnancy: abortion vs. completed pregnancy;
  - Breastfeeding status: breastfeeding vs. no breastfeeding.
- To evaluate the pregnancy, fetal and obstetrical outcomes of the pregnancies following breast cancer diagnosis in *BRCA* mutated patients.
- To evaluate the safety of ART procedures following breast cancer diagnosis in *BRCA* mutated patients.

- To evaluate the impact of anticancer therapies on patients' ovarian function, in terms of incidence of treatment-induced POF and age at menopause.
- To describe baseline, tumor and treatment characteristics as well as patterns of care including access to risk-reducing surgeries in *BRCA* mutated patients.
- To evaluate the prognostic impact of baseline, tumor and treatment characteristics as well as of risk-reducing surgeries in *BRCA* mutated patients.
- To evaluate tumor infiltrating lymphocytes (TILs) in *BRCA* mutated patients.

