##### Inclusion criteria:

- Diagnosis of invasive breast cancer between January 2000 and December 2020;
- Breast cancer diagnosis at the age of  $\leq 40$  years;
- Known presence of germline *BRCA* pathogenic variant.

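### Age at menopause has no censoring rule or estimator, so a summary of observed ages would be biased early and subgroup or historical differences could be spurious

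*Combined protocol and SAP*

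**What the plan says.** The secondary objective on ovarian function is framed "in terms of incidence of treatment-induced POF and age at menopause" (Section 2). Section 3.3 lists the data item as "Ovarian function after chemotherapy: treatment-induced POF; age at menopause". Section 4 restricts the analysis to women who received (neo)adjuvant chemotherapy and says that "incidence of treatment-induced POF and age at menopause will be evaluated, if available".

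The definition in Section 4 is "Age at menopause will be defined as age in which patients had absence of menses for" 12 months or more. For women whose menses came back and who were still cycling near their last visit, "they will not be considered as having developed menopause". Subgroups follow by age at diagnosis, type of chemotherapy and use of endocrine therapy. Then: "These results will be compared to historical data in the" BRCA wild-type breast cancer population. No source, length of follow-up or method is given for those data.

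The eligibility criteria (Section 3.1) set the age structure: "Breast cancer diagnosis at the age of" 40 or younger, and "Diagnosis of invasive breast cancer between January 2000 and December 2020".

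The only explicit censoring rule in Section 4 is for DFS. A general sentence near its end assigns Kaplan-Meier methods to time-to-event outcomes. It does not name age at menopause and gives no age scale, entry time or censoring rule for it.

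**The concern.** A woman still menstruating at last contact has no age at menopause. If the analysis summarises the ages that exist, it describes only women whose menopause came early enough to be seen. In a cohort diagnosed at 40 or younger, many will be last seen before the usual age of menopause, so this selection is strong.

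The bias is also uneven. It depends on how old a woman is at last contact, and so on age at diagnosis, calendar year of diagnosis and length of follow-up. Age at diagnosis is a planned subgroup factor. Type of chemotherapy is another; if regimens changed over the 20 years of diagnoses (an assumption), the regimen used later would tend to show an earlier menopause for that reason alone. The historical comparison adds a second group with its own unknown truncation.

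At stake is the reading of a secondary objective: whether cancer therapy brings menopause forward in BRCA carriers. A value a few years early could come from the length of follow-up, with no effect of treatment or of BRCA status.

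**Working it through.** The plan gives no figure for age at menopause, so there is none to reproduce.

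**Inputs from the documents.** Diagnosis at 40 or younger, in 2000-2020 (Section 3.1). Protocol version 2.0 is dated January 2022, with 4 months for data collection per institution (Section 3.2), so last contact around 2022 is an inference. The power statement in Section 4 gives a total duration of 2000-2030, so 2030 is run as well.

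**Assumptions.** Age at diagnosis about normal (mean 34.5, SD 4, none above 40); diagnoses uniform over the period; true age at menopause normal with mean 50, SD 4, in every woman; loss to follow-up of 0 to 10% per year; no surgery; no treatment effect.

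**Step 1: hand check.** For women all last seen at age L, the mean observed age is μ − σ·φ(z)/Φ(z), with z = (L − μ)/σ. (Truncation at diagnosis is negligible here: at age 40, z = −2.5 and Φ = 0.6%.) With μ = 50 and σ = 4:
- L = 45: z = −1.25; 50 − 4 × 0.1826/0.1056 = 43.1
- L = 50: z = 0; 50 − 4 × 0.3989/0.5 = 46.8
- L = 55: z = 1.25; 50 − 4 × 0.1826/0.8944 = 49.2

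The true mean is 50 in each row; only age at last contact differs.

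**Step 2: the whole cohort, by simulation.**

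| Last contact | Mean of observed ages | Too early by |
|---|---|---|
| 2022 | 46.7 (10% loss) to 47.8 (no loss) | 50.0 − 46.7 = 3.3; 50.0 − 47.8 = 2.2 |
| 2030 | 47.6 (10% loss) to 48.9 (no loss) | 50.0 − 47.6 = 2.4; 50.0 − 48.9 = 1.1 |

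With last contact in 2022, only 9 to 30% of women have a value.

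*Sensitivity.* With SD 4, no loss and three other shapes or spreads of age at diagnosis (uniform 25-40, about normal, skewed to 40), the bias for 2022 is 2.3-2.5 years for a true mean of 51, 1.9-2.1 for 49 and 1.2-1.5 for 45. For 2030 it is 0.6-1.3 years over the same cases.

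**Step 3: subgroups.** Same true mean of 50 in everyone, last contact 2022, no loss:
- Diagnosed at 30 or younger: 45.3. Diagnosed over 35: 48.3. False difference 48.3 − 45.3 = 3.0 years. (With 10% loss: 47.0 − 44.6 = 2.4.)
- Diagnosed 2000-2009: 48.2. Diagnosed 2010-2020: 44.4.

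**Step 4: historical comparator.** True mean 51 in both groups, with a flat follow-up, the observed mean is 44.3 at 8 years, 45.5 at 10 and 47.8 at 15. A cohort followed for 10 years therefore looks about 2.4 years earlier than one followed for 15, no different from one followed for 10, and about 1.2 years later than one followed for 8 (the last two figures are from unrounded means).

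**Step 5: does censoring repair it?** Under the Step 2 assumptions, the true proportion menopausal by 45 is Φ((45 − 50)/4) = Φ(−1.25) = 10.6%. A product-limit estimate on the age scale, with entry at diagnosis and censoring at last contact, returns 10.5-10.6% for both 2022 and 2030 and at each loss rate. In the sensitivity runs the Kaplan-Meier median is 51.0 for a true 51 and 49.0 for a true 49.

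**The case against.** The best reply is that Section 4 defines a variable and names no mean, median or analysis set for it. Kaplan-Meier is the stated general method for time-to-event outcomes, and the plan already uses it for a non-survival event, the rate of pregnancy. That stands so far: a reader might infer that the plan intends to discard women still menstruating, but the documents do not say so. The defect is an unassigned estimator and censoring rule. The general sentence does not cure it, because it leaves out this outcome, the age scale and the entry time.

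Two stronger readings are also tempting. One is that most women are under 50 at last contact. The documents give neither an age distribution nor a last-contact date. It is likely if contact ends around 2022, but not if follow-up runs to 2030 with little loss. The other is that the result will look like ovarian damage. That would need a historical series that is older or followed for longer, and Section 4 describes only a wild-type breast cancer population, which may be truncated in the same way. Step 4 shows that the false difference can go either way.

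Two further objections stand and shape the fix. First, Section 1 notes that salpingo-oophorectomy is generally recommended to carriers, and the definition as worded would count surgical menopause. As an illustration, if 60% had surgery at about 41, the mean would be roughly 0.6 × 41 + 0.4 × 50 = 44.6, a larger shift than the truncation bias. Second, Section 3.3 collects items where available and does not list menstrual status at last contact, so still menstruating and not recorded may be hard to separate.

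Finally, this is one half of one secondary objective. Treatment-induced amenorrhea, with its 12-month definition, and the primary DFS and pregnancy-rate analyses are not affected.

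**Conclusion.** The concern holds as a gap in specification with a predictable direction of bias. If observed ages are summarised, which the current wording allows, the result is too early in every scenario run. Under an assumed true mean of 50 (SD 4) the size is about 2 to 3 years for last contact around 2022 and about 1 to 2.4 years for 2030. Differences by age at diagnosis of about 2.4 to 3 years can arise with no real difference (last contact 2022).

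The sizes rest on the assumed distributions of age at diagnosis, true menopausal age and loss to follow-up, and on leaving surgery out. The direction does not depend on those values. For the historical comparison no direction can be claimed: without the comparator's follow-up and method, the difference cannot be interpreted. The point should be settled before analysis, but it does not touch the primary conclusions.

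**What to change.** In Section 4, where age at menopause is defined:

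1. Analyse it as a time-to-event outcome on the age scale, with delayed entry at age at diagnosis, or at the end of chemotherapy if that date is available.
2. Censor women known not to be menopausal at last contact. Report women with unrecorded menstrual status separately, and do not treat them as still menstruating.
3. Treat prophylactic gynecological surgery (use and date are collected, Section 3.3) as a censoring or competing event, and state which, so that surgical menopause is not counted as an effect of chemotherapy.
4. Report the cumulative proportion menopausal at fixed attained ages, for example 40 and 45, overall and by subgroup, in place of a mean or median among menopausal women.
5. Compare with historical data only where the same method and attained ages are available. Otherwise drop that comparison for this outcome.

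The cost is mainly wording. Age at diagnosis, age at menopause, date of last follow-up and date of surgery are already on the collection list. Menstrual status at last contact and the end-of-chemotherapy date are not listed explicitly, so the data file should be checked for them. The downsides are that a median may not be estimable and that records without menstrual status reduce the usable sample.
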